5.1 Sub-studies

Seattle Children's Hospital R21

An R21-funded sub-study titled, “Differences in infecting and colonizing Enterobacteriaceae from short-course vs. standard therapy of pediatric UTI” is currently planned with collaborators at Seattle Children’s Hospital. This sub-study hypothesizes that both the antibiotic agent and the length of therapy will affect the patients’ indigenous flora and thus affect both the likelihood of recovering *E. coli* and/or *K. pneumoniae* from stool and the resistance phenotypes of the recovered isolates. The sub-study will utilize PCR- and sequence-based methods to characterize phylogenetic and resistance properties of the recovered isolates. The sub-study will also test the hypothesis that (1) *E. coli* and *K. pneumoniae* recovered from 2 or 3 stool cultures are more likely to be members of disease-associated subgroups within their respective species (*E. coli* phylogroups B2 and D, *K. pneumoniae* cluster Kpl); (2) treatment-susceptible strains recovered from cultures during treatment (culture #1 for 5-day arm; cultures #1 or #2, 10-day arm) are more likely to be members of disease-associated subgroups; (3A) treatment-resistant strains of either species are more likely than treatment susceptible strains to be recovered from cultures during treatment; and (3B) treatment susceptible strains of either species are more likely to be recovered from cultures during treatment in the AMC arm than in the TMP/SMX or CFX/CFD arms.

Carbapenem resistant enterobacteriaceae

For each enrolled research subject, the stool or perirectal swab collected at the Test of Cure visit will also be utilized to perform additional screening for the presence of carbapenem resistant enterobacteriaceae. The results of this additional screening will be used to determine the prevalence of colonization with carbapenem-resistant Enterobacteriaceae (overall and for specific pathogens) in ambulatory children after completion of treatment for UTI.

Microbiome pilot study

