12 STATISTICAL CONSIDERATIONS

12.1 Study Objectives

Primary Objective:

To determine if halting antimicrobial therapy in subjects who have exhibited clinical improvement 5 days after starting antibiotic therapy (short course therapy) have the same failure rate (symptomatic UTI) through TOC (visit Day 11-14) as subjects who continue to take antibiotics for an additional 5 days (standard course therapy).

Secondary Objectives:

To determine if short-course therapy compared to standard course therapy results in similar numbers of children experiencing a recurrent infection (relapse and reinfection).

To determine if short-course therapy compared to standard course therapy results in similar numbers of children with asymptomatic bacteriuria.

To determine if short-course therapy compared to standard course therapy results in similar numbers of children with gastrointestinal colonization of antimicrobial resistant *Escherichia coli* (*E. coli*) and *Klebsiella pneumoniae* (*K. pneumoniae*).

To determine if short-course therapy compared to standard course therapy results in similar numbers of children with clinical symptoms that may be related to a UTI.

To determine if short-course therapy compared to standard course therapy results in similar numbers of subjects with positive urine cultures prior to or at the TOC visit.

Sub-Study Objectives:

To determine if *E. coli* and *K. pneumoniae* recovered from 2 or 3 stool cultures are more likely to be members of disease-associated subgroups within their respective species (*E. coli* phylogroups B2 and D, *K. pneumoniae* clusterKpl)

To determine if treatment-susceptible strains recovered from cultures during treatment (culture #1 for 5-day arm; cultures #1 or #2, 10-day arm) are more likely to be members of disease-associated subgroups;

To determine if treatment-resistant strains of either species are more likely than treatment susceptible strains to be recovered from cultures during treatment

To determine the overall prevalence of colonization with carbapenem-resistant Enterobacteriaceae (overall and for specific pathogens) in ambulatory children after completion of treatment for UTI

To compare the overall biodiversity of the gut microbial community, as measured by culture-independent marker gene sequencing at each follow-up visit following short-course and standard-course antibiotic exposure.

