The secondary outcome measures of this trial are provided above. A difference between the two arms with regards to asymptomatic bacteriuria, presence of clinical symptoms, and negative urine culture is not expected. No difference will mean that shorter courses of antibiotics for treatment are not inferior to long courses in eradicating bacteria from the urinary tract as well as impacting clinical symptoms. This analysis will be a conventional test for efficacy and will consist of a straightforward two-sample test for a difference between proportions, using a two-sided chi-square test at significance level of .05.

Sub-study Analysis:

Seattle Children’s Hospital R21

As previously noted, patient stool samples will be collected on 3 occasions. For primary analysis, cross-sectional analysis will be performed, i.e. looking at samples from one occasion at a time.

For each occasion, the following proportions will be summarized:

- 1) Among all patients, proportion of patients with *E. coli* detected, proportion of patients with *K. pneumoniae* detected, and same proportions within each treatment arm.
- 2) Among patients with *E. coli* detected, proportions of sub-type 0 or sub-type 1; among patients with *K. pneumoniae* detected, proportions of the two sub-types, and same proportions within each treatment arm.
- 3) Among patients with *E. coli* detected, proportions of treatment-susceptible *E. coli*; among patients with *K. pneumoniae* detected, proportion of treatment-susceptible *K. pneumoniae*; and same proportions for different treatment arms.
- 4) Among patients with *E. coli* detected AND treatment-susceptible, proportions of sub-type 1; among patients with *K. pneumoniae* detected AND treatment-susceptible, proportions of sub-type 1; and same proportions for different treatment arms
- 5) Among patients with *E. coli* detected proportion of treatment-resistant *E. coli*; among patients with *K. pneumoniae* detected, proportion of treatment-resistant *K. pneumoniae*; and same proportions within different treatment arms.

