After obtaining the proportions listed in (2) above, a binomial test will be used to determine whether the proportion of *E. coli* sub-type 1 (phylogroups B2 and D) is significantly larger than 50%. A chi-square test will also be used to test the differences in proportions of sub-type 1 across treatment arms. In addition, a multivariable logistic regression on presence of sub-type 1 strains will be conducted. The same approach will be used for *K. pneumoniae* sub-type 1.

For culture #1 (5-day treatment arm), or culture #1 or #2 (10-day treatment arm), the proportions of sub-type 1 will be tested using a binomial test, then a logistic regression will be used to examine the association between presence of sub-type 1 strains and treatment arms.

A chi-square test will be used to examine the difference in proportions estimated in (3) and (5) above. Logistic regression models will also be used for analysis.

Microbiome pilot study

We will preprocess all marker-gene microbiome sequencing data using the Quantitative Insights Into Microbial Ecology (QIIME) software package [PMID: 20383131]. This will include performing sequence quality filtering and demultiplexing of reads to separate sequences by sample. For taxonomic marker gene and RNA-Seq sequences, we will stitch overlapping paired-end reads together after demultiplexing using PANDAseq [PMID: 22333067]. We will then map marker gene reads to 97% operational taxonomic units (OTUs) using the Greengenes [PMID: 22134646] reference database and the USEARCH [PMID: 20709691] reference mapping software wrapped by QIIME. We will measure within-sample biodiversity (alpha diversity) based on these OTUs using whole-tree phylogenetic diversity⁵⁶ and the Greengenes reference phylogeny. To quantify

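### The analysis described for R21 sub-study objective 1 tests overall sub-type 1 prevalence at one visit against 50%, not whether strains recovered from 2 or 3 cultures are more often disease-associated

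*Protocol*

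**What the plan says.** **Objective.** Protocol 12.1 asks whether the two species "recovered from 2 or 3 stool cultures are more likely to be members of disease-associated subgroups within their respective species". The same objective stands in Protocol 4.1 and in SAP 2.2.5 and 3.1, and Protocol 5.1 lists it as hypothesis (1) to be tested. None of these places says what the strains are to be compared with.

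**Analysis.** Protocol 12.4, Sub-study Analysis, says: "For primary analysis, cross-sectional analysis will be performed, i.e. looking at samples from one occasion at a time". Item 2 of its list then summarises, among patients with the species "detected, proportions of sub-type 0 or sub-type 1", overall and by arm. Three analyses follow for that proportion:

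- a binomial test of whether the *E. coli* proportion of "sub-type 1 (phylogroups B2 and D) is significantly larger than 50"%;
- a comparison by arm: "A chi-square test will also be used to test the differences in proportions of sub-type 1 across treatment arms";
- a regression with no covariates named: "a multivariable logistic regression on presence of sub-type 1 strains will be conducted".

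The same approach is to be used for *K. pneumoniae*.

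**SAP.** Section 4.2.4 lists the sub-type proportions by arm as an endpoint. It states that the sub-study plans are designed and executed outside the SCOUT protocol, and it takes them no further.

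**The concern.** The objective is about repeated recovery, so an analysis of it needs two things: a variable saying whether a strain was found once or in 2 or 3 cultures, and a group against which to judge whether it is more likely to be disease-associated. The described analysis has neither. Its denominator is every carrier at a single visit, and its reference value is a fixed 50% with no stated source. The same value is carried to a second species that has its own subgroup scheme.

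At stake is a stated hypothesis of the sub-study. If this test were reported as the answer to objective 1, the hypothesis could be declared supported because sub-type 1 is common in stool carriage generally, or declared unsupported because it is uncommon, whatever the relation with repeated recovery.

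**Working it through.** **Step 1: match objective to analysis.**

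| Element | Objective 1 | Protocol 12.4 as described |
|---|---|---|
| Strains studied | Recovered from 2 or 3 cultures | All carriers at one occasion |
| Grouping | Number of positive cultures (implied) | Treatment arm |
| Reference | Not stated | 50%, no basis given |

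One analysis does span more than one occasion: culture #1 in the 5-day arm, and culture #1 or #2 in the 10-day arm. It serves objective 2, which concerns strains recovered during treatment, and it too does not count positive cultures.

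**Step 2: what the 50% test responds to.** The documents give no sample size, significance level, power or expected sub-type 1 rate for this test, so there is no planned figure to reproduce. Every input below is an assumption: one-sided level 5%; n = 150, 250 or 400 children with *E. coli* at an occasion; overall sub-type 1 rate p of 45% or 60%.

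The exact test rejects when the sub-type 1 count X reaches r, the smallest integer with P(X ≥ r | n, 0.5) ≤ 0.05. The rejection probability at p is P(X ≥ r | n, p).

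| n | r | Size at 50% | p = 60% | p = 45% |
|---|---|---|---|---|
| 150 | 86 | 0.043 | 0.77 | 0.0016 |
| 250 | 139 | 0.044 | 0.93 | 0.0005 |
| 400 | 217 | 0.049 | 0.99 | 0.0001 |

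**Step 3: no association.** Let 60% of strains be sub-type 1 both among those recovered repeatedly and among those recovered once. Objective 1 is then false when judged against strains recovered once, yet at n = 250 the test rejects in 93% of studies.

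**Step 4: true association.** Let 40% of strains be recovered repeatedly, with sub-type 1 in 60% of those and 35% of the rest. The overall rate is 0.4 × 0.60 + 0.6 × 0.35 = 0.24 + 0.21 = 0.45. At n = 250 the test rejects in about 0.05% of studies.

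**Step 5: a direct comparison on the same assumptions.** With 100 repeated and 150 single recoveries:

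- difference = 0.60 − 0.35 = 0.25
- pooled standard error = √[0.45 × 0.55 × (1/100 + 1/150)] = 0.0642
- unpooled standard error = √[0.60 × 0.40/100 + 0.35 × 0.65/150] = 0.0626
- two-sided 5% power = Φ[(0.25 − 1.96 × 0.0642)/0.0626] = Φ(1.98) ≈ 0.98

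A second case uses 50% against 30%, again with 40% repeated, so the overall rate is 0.4 × 0.50 + 0.6 × 0.30 = 0.38. At n = 200 the direct comparison has power 0.82, and the 50% test rejects with probability 0.000.

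**The case against.** The strongest reply is that the documents do not claim to hold the full plan. SAP 4.2.4 places the sub-study plans outside the SCOUT protocol, and Protocol 12.4 calls itself a general description. It also says "For primary analysis, cross-sectional analysis will be performed, i.e. looking at samples from one occasion at a time", which leaves room for further analyses, and the regression names no covariates, so recovery count is not ruled out. This stands as a limit on the claim. A reader might infer that objective 1 will never be properly analysed, or that the sub-study cannot answer it. The documents support neither inference. They show only that the analysis described in them does not address the objective.

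A second reply is that, with a two-level sub-type, 50% may mean more likely than not, and the objective names no other comparator. It is therefore too strong to call 50% arbitrary; what can be said is that no basis is given. The reply does not rescue the test, which would still use all strains at one visit and not those recovered from 2 or 3 cultures.

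A third is that 2 or 3 might mean culture #2 or culture #3. The next objective uses number signs when it means particular cultures, so this is the less likely reading.

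Finally, the figures are all assumed. They show what the test responds to and do not estimate error in this sub-study.

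**Conclusion.** The point holds as a mismatch between a stated hypothesis and the test described for it. As written in Protocol 12.4, the test for objective 1 reflects how common sub-type 1 is among all carriers at a visit and does not measure the association with repeated recovery. Under the assumed inputs (one-sided 5%, n = 250), it rejects in 93% of studies with no association at a 60% rate, and in about 0.05% at a 45% rate despite enrichment. Other values of n or of the rate change these figures but not the reason for them.

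The reach is limited to this sub-study. A reader might take the point as a weakness in the trial's main results, but the sub-study outcomes do not enter the primary endpoint or the five secondary endpoints. If a separate sub-study plan already defines repeated recovery and its comparator, what remains is to bring Protocol 12.4 into line with it or refer to it.

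**What to change.** 1. State the comparator in objective 1, for example strains recovered from only one culture.
2. For each child and species, classify strains as recovered once or in 2–3 cultures, matching them across visits by the typing already planned. Matching is needed because a child may carry sub-type 0 at one visit and sub-type 1 at another.
3. Restrict this analysis to children with at least two stool samples, and account for the number of samples obtained. Under Protocol 8.3 and Table 4, children who fail before test of cure need not attend that visit and give no stool at unscheduled visits, so they have fewer chances of repeated recovery.
4. Compare the sub-type 1 proportion between the two groups as a difference with a confidence interval. Fit the planned logistic model with recovery count, arm and antibiotic as covariates, allowing for clustering within child.
5. Keep the test against 50% only as descriptive, or justify the value separately for each species.
6. If a separate sub-study plan already does this, cite it in Protocol 12.4.

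The cost is wording, to be agreed with the sub-study investigators. The isolates and typing are already planned, and Protocol 16.2 foresees no additional data sources. The downside is fewer informative children than in a single-occasion analysis.

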4 OBJECTIVES

4.1 Study Objectives

The primary and secondary objectives of this study are as follows:

Primary Objective:

To determine if halting antimicrobial therapy in subjects who have exhibited clinical improvement 5 days after starting antibiotic therapy (short course therapy) have the same failure rate (symptomatic UTI) through TOC (visit Day 11-14) as subjects who continue to take antibiotics for an additional 5 days (standard course therapy).

Secondary Objectives:

To determine if short-course therapy compared to standard course therapy results in similar numbers of children experiencing a recurrent infection (relapse and reinfection).

To determine if short-course therapy compared to standard course therapy results in similar numbers of children with asymptomatic bacteriuria.

To determine if short-course therapy compared to standard course therapy results in similar numbers of children with gastrointestinal colonization of antimicrobial resistant *Escherichia coli* (*E. coli*) and *Klebsiella pneumoniae* (*K. pneumoniae*).

To determine if short-course therapy compared to standard course therapy results in similar numbers of subjects presenting with clinical symptoms that may be related to UTI.

To determine if short-course therapy compared to standard course therapy results in similar numbers of subjects with positive urine cultures up to and including TOC.

Sub-Study Objectives:

Seattle Children’s Hospital R21

To determine if *E. coli* and *K. pneumoniae* recovered from 2 or 3 stool cultures are more likely to be members of disease-associated subgroups within their respective species (*E. coli* phylogroups B2 and D, *K. pneumoniae* clusterKpl).

To determine if treatment-susceptible strains recovered from cultures during treatment (culture #1 for 5-day arm; cultures #1 or #2, 10-day arm) are more likely to be members of disease-associated subgroups.

To determine if treatment-resistant strains of either species are more likely than treatment susceptible strains to be recovered from cultures during treatment.

Carbapenem resistant Enterobacteriaceae study

To determine the overall prevalence of colonization with carbapenem resistant Enterobacteriaceae in children after completion of the course of antibiotic therapy for UTI

Microbiome pilot study

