8.2 Enrollment Visit (Day 2-6 from start of prescribed antibiotics)

Prior to taking the sixth day of prescribed treatment

The Study Nurse/Nurse Practitioner/Physician will discuss the SCOUT Study, the goal, the study procedures and risks with the parent(s)/legal guardian(s); answer any questions and address any concerns that they have; have the parent(s) or guardian(s) sign the informed consent form and the child sign the assent form (if \geq seven years of age and enrolled at CHOP) if applicable prior to any study procedures being performed. Study Nurses/Nurse Practitioners/Physicians will also administer the eligibility questionnaire; administer a symptom questionnaire to confirm by history clinical

improvement (afebrile within 24 hours and asymptomatic [absence of dysuria in all children; absence of suprapubic, abdominal or flank pain, urinary urgency, frequency, hesitancy, dysuria in children >2 years and absence of poor feeding or vomiting in children >2 months to 2 years]); take the child’s temperature; and perform a targeted pain assessment for any suprapubic, abdominal, or flank pain/tenderness. In addition, a baseline stool sample will be collected and concomitant medications will be reviewed.

The written consent and assent documents, acquired from subject’s parent(s) or legal guardian(s) and subject (if age seven or older and enrolled at CHOP) before any study procedures are performed and the child is enrolled in the study, will describe potential risks and benefits of study participation as well as the responsibilities of the study participants, parent(s) or legal guardian(s), and study investigators. This assent document will be written in language understandable to the child (age seven or older).

At the Enrollment Visit, after a potential subject has met the study eligibility criteria, including exhibiting clinical improvement (afebrile and asymptomatic), the child will be given a random treatment assignment to either short-course or standard-of-care therapy. Subjects will be randomized based on the responses of the Study Nurse/Nurse Practitioner or Physician to the WesTrax™ interactive voice response (IVR) system. The system will stratify randomization based on whether:

- (1) The UTI was originally associated with fever and
- (2) The antibiotic prescribed at initiation of therapy.

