If the Enrollment Visit occurs at any time prior to completion of the day 5 dosing of prescribed antibiotic treatment, the child’s parent(s)/legal guardian(s) will be advised to complete their originally prescribed medication through day five. The subject would start study product on Day 6 and continue through Day 10. For these subjects enrolled prior to Day 5, confirmation from the parents will be obtained on Day 5 or Day 6 (prior to taking the first dose of SCOUT therapy on Day 6) that the subjects remain afebrile and have not had worsening of symptoms. Any volunteer that develops a fever or worsening symptoms prior to initiating study treatment will be considered an entry failure. If the Enrollment Visit occurs on Day 6, the Study Coordinator will clearly explain that the Enrollment Visit can only occur on Day 6 of antibiotic treatment if the child has not yet started the Day 6 dose of the initially prescribed antibiotics. The Study Nurse/Nurse Practitioner/Physician will confirm (at the Enrollment Visit) that the child has not yet started their Day 6 dose of prescribed antibiotics prior to enrolling them through the “Enrollment Visit Case Report Form.”

The Study Nurse/Nurse Practitioner/Physician will review the contents of the study product kit with the child’s family, review the need to complete the study product at the dose and frequency indicated and teach them how to complete the medication diary to document adherence.

Parents will be educated at the time of their child’s enrollment in the study about the potential sequelae of untreated UTI and the benefits of prompt and adequate treatment. They will be instructed to (1) contact primary care providers and study personnel in the event of intercurrent febrile illness, (2) have their child evaluated within 36 hours by a SCOUT study physician or the child’s primary care provider and (3) have a urine sample obtained to evaluate for the presence of UTI. The study nurses, nurse practitioners and the investigators at each site will be available on a 24-hour basis, through a study-dedicated cellular phone.

Stool specimens will be collected either by inoculation of a sterile dacron-tipped swab into stool in a diaper, or by insertion of a swab into the distal rectum (similar to obtaining a rectal temperature) where it will be held in this position for five seconds.

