8.3 Test of Cure (TOC) Post Treatment Visit

Day 11 – 14 (one – four days after completing the study product)

Subjects will return for a follow-up visit two – four days after completing the study product. At this follow-up visit, a Study Nurse/Nurse Practitioner/Physician will perform assessments of the subjects. Using a standardized interview form (symptom questionnaire), the subjects and/or their parent(s) or legal guardians will be asked to provide a subjective evaluation of the presence or absence of UTI symptoms and possible side effects of the antibiotic like diarrhea or a rash. Parent(s) or legal guardian(s) will also be asked to report any inter-current illnesses (e.g., upper respiratory infection, pharyngitis, otitis media, sinusitis), the name and duration of concomitant therapy, and potential side effects of study product. They will also be asked if the subject sought medical care for possible recurrence of UTI, the records of the encounter including microbiology culture results will be obtained so the SCOUT Study physician,

nurse practitioner or nurse can follow up with the child’s parent(s)/legal guardian(s) and PCP. The Study Nurse/Nurse Practitioner/Physician will collect a second stool sample, the medication diary and the study product bottle. Subjects at CHOP who agree to the Microbiome sub-study will have additional peri-rectal, anal, and stool swabs collected, if applicable. The subject’s temperature will also be taken and the child will be assessed for any suprapubic, abdominal, or flank pain or tenderness. In addition, the Nurse will collect a urine sample for urinalysis and culture from all subjects. The Study Nurse/Nurse Practitioner/Physician will use the bag technique on asymptomatic infants and young children (before they are toilet trained) and the clean catch technique for older toilet trained children. For symptomatic infants and young children a urine sample will be obtained using the clean catch technique (or catheterize if unable to capture with clean catch).

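### Seattle R21 sub-study: the supplementary on-treatment analysis counts one stool culture in the 5-day arm but two in the 10-day arm before comparing arms, and the second culture is post-treatment

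*Protocol*

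**What the plan says.** Protocol 12.4 (Sub-study Analysis, Seattle R21) sets out the culture sets: "For culture #1 (5-day treatment arm), or culture #1 or #2 (10-day treatment arm), the proportions of sub-type 1 will be tested". The test named there is binomial. The same sentence adds that "a logistic regression will be used to examine the association between presence of sub-type 1 strains and treatment arms". Protocol 4.1 gives the label for this set: strains "recovered from cultures during treatment (culture #1 for 5-day arm; cultures #1 or #2, 10-day arm". The same definition appears in the Protocol Summary (sub-study outcome measures), in Protocol 5.1 and 12.1, and in SAP 2.2.5 and 3.1.

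The visit schedule fixes the timing. At the Enrollment Visit (Protocol 8.2, Day 2–6, before any Day 6 dose) "a baseline stool sample will be collected and concomitant medications will be reviewed"; this is culture #1. On randomised treatment, 8.2 says: "The subject would start study product on Day 6 and continue through Day 10". At the Test of Cure visit (8.3) staff "will collect a second stool sample, the medication diary and the study product bottle"; this is culture #2. The heading line of 8.3 times that visit as "Day 11 – 14 (one – four days after completing the study product". The next sentence gives two to four days instead, but either range falls after dosing.

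Protocol 12.4 also says that the primary approach for this sub-study is cross-sectional, one stool occasion at a time, with proportions by arm. SAP 4.2.4 leaves sub-study analyses to their own investigators and does not discuss them further.

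**The concern.** An arm comparison needs the same measurement in both arms. Here the measurement is one stool in one arm and up to two in the other. Culture #1 cannot carry an effect of duration, because both arms are still on the clinician's prescription when it is taken. Any expected arm difference in this analysis can therefore enter only through culture #2, which is counted in the 10-day arm alone. The 5-day arm's culture #2 is scheduled (Protocol 9.2.3.1 takes stool at all three visits) but is not used in this paragraph.

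The label is also wrong on the protocol's own dates. In the 10-day arm, culture #2 comes one to four days after the last dose. In the 5-day arm, whose active antibiotic ends on Day 5, it comes six to nine days after (11 − 5 = 6; 14 − 5 = 9).

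What is at stake is the reading of a stated sub-study objective. An excess of disease-associated strains in the longer-course arm could be reported as selection by treatment when it reflects the number of cultures counted.

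**Working it through.** The documents give no rate, power or sample size for this comparison, so there is no stated figure to reproduce.

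**Inputs from the documents.** Culture sets by arm and the regression (12.4); timing (8.2, 8.3); 1:1 allocation and 672 evaluable children (Protocol Summary; section 5), so 672 / 2 = 336 per arm as an upper bound for the sub-study.

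**Assumptions, not in the documents.** Per-culture prevalence *p* of sub-type 1, the same in both arms and at both visits (no effect); within-child correlation ρ between cultures; two-sided 5% test. The regression on arm is approximated by a two-proportion test.

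**Reading 1: child is the unit, positive if either culture is positive.**

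5-day arm: *p*. 10-day arm: 1 − [(1 − *p*)² + ρ·*p*(1 − *p*)].

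For *p* = 0.5 and ρ = 0.8: 1 − [0.25 + 0.8 × 0.25] = 1 − 0.45 = 0.55. The odds ratio is (0.55/0.45)/(0.50/0.50) = 1.22.

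| ρ | 5-day | 10-day | Odds ratio | False-positive rate, 336 per arm | 100 per arm |
|---|---|---|---|---|---|
| 1 | 50% | 50% | 1.00 | 5% | 5% |
| 0.9 | 50% | 52.5% | 1.11 | 10% | 6% |
| 0.8 | 50% | 55% | 1.22 | 25% | 11% |
| 0.5 | 50% | 62.5% | 1.67 | 91% | 43% |
| 0 | 50% | 75% | 3.00 | about 100% | 96% |

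At *p* = 0.3 the 10-day figure is 34.2%, 40.5% or 51% for ρ = 0.8, 0.5 or 0, against 30%. At *p* = 0.2 with 336 per arm the false-positive rate is 17%, 68% and 99.7% for the same ρ.

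The direction does not depend on *p*: the chance of a positive in #1 or #2 is never below the chance in #1 alone. With all children in the denominator, the 10-day arm's expected proportion therefore cannot fall below the 5-day arm's.

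If the denominator is children with *E. coli* detected (detection 0.3–0.8, sub-type share 0.3–0.5), the spurious gap is about 1 to 20 points for sub-type correlation 0 to 0.8, and zero at perfect concordance.

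The binomial test is affected too. Suppose the 50% null stated for the main sub-type test also applies here. With 336 children and a true per-culture share of 50%, the one-sided test in the 10-day arm rejects 56% of the time at ρ = 0.8 and 99.8% at ρ = 0.5. Its actual size for a single culture is 4.5%.

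**Reading 2: isolate is the unit.**

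With a stable sub-type share, the simulated arm difference is zero. The false-positive rate is 7%–10% for ρ from 0.5 to 1, because only the 10-day arm contributes paired cultures.

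If the share shifts by *t* between cultures in both arms, the 10-day arm averages *p* + *t*/2, so the arm difference is *t*/2. A 10-point shift gives 5 points. With 336 against 672 isolates treated as independent, the standard error is √(0.50 × 0.50/336 + 0.55 × 0.45/672) = 0.033, the ratio is about 1.5, and the test rejects about 32% of the time.

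**After the change.** With the same cultures in both arms on Reading 1 (*p* = 0.5, 336 per arm), the expected difference is zero and simulated rejection is 4.6%–5.0% for ρ from 0 to 0.8.

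**The case against.** The strongest reply is that the sub-study does not rest on this paragraph. Section 12.4 makes the one-occasion-at-a-time analysis primary and tests sub-type 1 across arms there, with the same culture in both arms. That stands. A reader might infer that the sub-study's arm comparison as a whole is biased, and the documents do not support that inference.

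Second, the unit of analysis is not defined. The objective speaks of strains, and other items in 12.4 condition on detection, so an isolate-level analysis is a fair reading. On that reading, with a stable sub-type share, the difference itself is unbiased. A reader might infer that an arm difference must appear whenever there is no effect. That holds only for per-child scoring, and even then not if the cultures always agree. The isolate reading still needs clustering handled.

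Third, independence between two stools from one child is the least plausible case. Protocol 2.1 describes colonisation with resistant *E. coli* lasting months, which points towards concordance. The 50% vs 75% figure is therefore an extreme, not an expectation.

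Fourth, 12.4 calls itself a general description, and SAP 4.2.4 places sub-study plans elsewhere, so a fuller plan may exist. That limits the weight of the point. It does not remove it: among these documents 12.4 is the only plan for this regression, and nothing here corrects it.

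**Conclusion.** The paragraph is wrong as written, within a narrow scope. The two arms contribute different sets of cultures, the arms are compared on those sets, and culture #2 is not on treatment in either arm. These are facts of the text.

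The size is not known. With per-child scoring and an assumed 50% prevalence, the built-in excess in the 10-day arm is 5 points at correlation 0.8, 12.5 at 0.5, and 25 if the cultures were independent. With isolates as the unit, the difference is biased only if the sub-type share moves over time, and the test is modestly anti-conservative otherwise. Prevalence, correlation and sub-study sample size are all assumptions.

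The trial's primary and secondary endpoints and the sub-study's cross-sectional analysis are not touched. The correction is still worth making, because the paragraph serves a stated objective and the asymmetry is easily removed.

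**What to change.** In this paragraph of 12.4:

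- Use the same cultures in both arms. Either take the arm contrast from culture #2 vs #2 (and #3 vs #3), as the cross-sectional analysis already does, or fit a repeated-measures model with visit as a factor and within-child clustering.
- Answer the on-treatment question from culture #1 pooled over arms, since it is the only culture taken on antibiotic in both.
- State the unit of analysis (child or isolate) and the denominator.
- Relabel culture #2 as post-treatment in the Protocol Summary, Protocol 4.1, 5.1 and 12.1, and SAP 2.2.5 and 3.1.

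The cost is wording only; no new specimen or visit is needed. There is one small downside. It would be wrong to assume that culture #2 is complete in both arms: children who fail before Test of Cure need not attend that visit, and no stool is taken at the interim visit (Protocol Summary; 8.3). At the failure rates of 5% to 9% used in Protocol 12.2, failures up to and including Test of Cure would number about 17 to 30 of 336 per arm (336 × 0.05 = 16.8; 336 × 0.09 = 30.2). That is an upper bound for cultures lost this way. Because this missingness depends on outcome, report it by arm.
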